4.2 Safety variables

4.2.1 Primary safety variables

- Adverse events throughout the study
- Subject withdrawals due to AEs

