12.4.1 Analysis of safety variables

Descriptive statistics for the safety variables will be presented by cohort and infusion duration, cohorts overall, and all subjects overall. Additional summaries will include a summary of the OLB, RXB, IOB, and IIB groups by cohort and infusion duration.

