12.4.1.1 Primary safety variables

Adverse events will be coded using the Medical Dictionary for Regulatory Activities (MedDRA[®]). Adverse events will be summarized by MedDRA System Organ Class and Preferred Term.

The primary safety variables will be summarized for the iv PK Period for the SS-iv. Summaries of adverse events will also be presented by study period for the SS and epochs relative to bolus/infusion for the SS-iv.

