#### 2.2.2 Safety variables

##### 2.2.2.1 Primary safety variables

- Adverse events (AEs) throughout the study
- Subject withdrawals due to AEs

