### **3.10 Changes to protocol-defined analysis**

As iv BRV is defined as the study medication the following parts of the PK-PPS definition were further clarified: "subjects in the SS-iv" instead of "subjects in the SS" and "infusion times" instead of "intake times". Furthermore, the term "without important protocol deviations impacting the interpretability of the PK analyses" was added to the definition of PK-PPS.

Vital sign and ECG summary tables will summarize the subject data for each timepoint but not as stated in the protocol (pre-bolus/infusion period, the bolus/infusion period, the period immediately post-bolus/infusion, and period between each subsequent bolus/infusion). Adverse events tables will not summarize the subject data as specified in the protocol (pre-bolus/infusion period, the bolus/infusion period, the period immediately post-bolus/infusion, and period between each subsequent bolus/infusion). Instead AEs will be summarized by time relative to most recent bolus/infusion start time ( $\leq 5$  minutes,  $> 5$  to  $\leq 15$  minutes,  $> 15$  to  $\leq 60$  minutes,  $> 60$  minutes to  $\leq 12$  hours and  $> 12$  hours).

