## 10.2 Adverse Events

All adverse events (AEs) occurring during EP0065 (ie, after signing of the ICF) must be reported. For subjects who transition to study N01266, any AEs which began after the first dose of BRV in N01266 but prior to TC-1 of EP0065 will be considered as during EP0065 and N01266. Pre-treatment adverse events (PTAEs) are defined as AEs that had onset strictly prior to the date/time of the first BRV medication taken during EP0065. For OLB subjects, where the AE started prior to EP0065 enrollment, information will come from the respective OLB study.

Treatment-emergent adverse events (TEAEs) are defined as those events which started on or after the first BRV medication taken during the EP0065 study. Subjects who began the study on BRV treatment (OLB and RxB subjects) will be assumed to have taken BRV treatment on the first day of screening. Timing of an AE being treatment emergent varies by subject group: all AEs are treatment emergent for RxB and OLB subjects; all AEs on or after the IOB Treatment Period are treatment emergent for IOB subjects; all AEs on or after the iv PK Period are treatment emergent for IIB subjects.

Data handling rules for management of missing or partial start or stop dates for adverse events should follow those defined in the [Section 4.2.4](#). The classification of TEAE will be done after imputation of any partial start dates.

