### 10.2.1 AE summaries

All AE tables will be summarized separately over all AEs and by MedDRA SOC and MedDRA PT. The number and percentage of subjects experiencing each event at least once will be summarized. All summaries will be sorted alphabetically by SOC and by frequency of events within PTs, starting with the most frequent event overall. All summaries are for all study periods combined (Screening, IOB treatment, iv-PK, Follow-up, and Safety (BRV free) Period) unless otherwise indicated. Only the first occurrence of a TEAE of a particular PT will be included in incidence calculations, but all occurrences of TEAEs of the same PT will be included in counts of TEAEs. For summaries by study period, AEs are assigned only to the period on which they began. TEAEs of interest is a selection of TEAEs identified by UCB to be of interest to BRV.

The following summaries will be produced overall and by age cohort, for all subjects and separately by infusion duration, and subject group for the SS-iv:

- Incidence of AEs – Overview (number and percentage of subjects with at least one: AE, TEAE, serious TEAE, non-serious TEAE, TEAE of interest, TEAE requiring dose change,

drug-related TEAE, drug-related serious TEAE, and severe TEAE, as well as the number and percentage of subjects who discontinued due to a TEAE, had permanent withdrawal of BRV due to a TEAE, had an AE leading to death, and had a TEAE leading to death)

- Incidence of TEAEs
- Incidence of TEAEs Leading to Study Discontinuation
- Incidence of Serious TEAEs

The following AE summaries will be produced overall and by age cohort, for all subjects and separately by infusion duration for the SS-iv:

- Incidence of PTAEs
- Incidence of TEAEs by Maximum Intensity  
Each subject will be counted at most once per primary SOC or PT according to the maximum intensity of all AEs within that SOC or PT. Severe intensity will be assumed for AEs for which intensity is not specified.
- Incidence of TEAEs by Maximum Relationship  
Drug-related AEs are AEs for which the relationship to trial medication is specified as related or AEs for which relationship is not specified.
- Incidence of TEAEs of Interest
- Incidence of Non-serious TEAEs Occurring in at least 5% of Subjects
- Incidence of Serious TEAEs by Relationship to BRV
- Incidence of Fatal TEAEs by Relationship to BRV

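### SAP 10.2.1 does not place the iv PK Period summary of the primary safety variables on the SS-iv as protocol 12.4.1.1 specifies, and its time-since-infusion TEAE table does not name infusion duration

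*SAP*

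**What the plan says.** Protocol 12.4.1.1 makes three commitments for adverse events. The first is "The primary safety variables will be summarized for the iv PK Period for the SS-iv". The other two follow in the next sentence: "Summaries of adverse events will also be presented by study period for the SS and epochs relative to bolus/infusion for the SS-iv". Protocol 12.4.1 sets the layout: "Descriptive statistics for the safety variables will be presented by cohort and infusion duration, cohorts overall, and all subjects overall". The first primary safety variable is "Adverse events throughout the study" (protocol 4.2.1), repeated in SAP 2.2.2.1 as "Adverse events (AEs) throughout the study". The second is subject withdrawals due to AEs.

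SAP 10.2.1 sets the default period: "All summaries are for all study periods combined (Screening, IOB treatment, iv-PK, Follow-up, and Safety (BRV free) Period) unless otherwise indicated". None of the SS-iv incidence tables it lists is restricted to the iv PK Period. The by-period tables (TEAEs, TEAEs leading to study discontinuation, serious TEAEs, maximum intensity, maximum relationship) are by cohort and infusion duration, but are assigned to the SS.

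SAP 3.10 declares one change for adverse events, the replacement of the protocol's infusion epochs: "Instead AEs will be summarized by time relative to most recent bolus/infusion start time". SAP 10.2.1 lists the resulting table for the SS-iv, for all subjects and by age cohort.

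**The concern.** AEs and withdrawals due to AEs are the primary safety variables, and the study objective names the two infusion modes. A reader looking for the summary in protocol 12.4.1.1 will not find it on the set the protocol names, and SAP 3.10 does not say why.

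The all-period SS-iv tables are not the same thing. In SAP 10.2, "all AEs are treatment emergent for RxB and OLB subjects", and for IOB subjects TEAEs count from the start of oral dosing. These tables can therefore include TEAEs that began before any infusion.

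The table by time since infusion is the SAP's substitute for the protocol's separation of during-infusion from post-infusion time. If it pools the 15-minute and bolus subjects, it no longer makes that separation.

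**Working it through.** The plan gives no figure to reproduce. The first step compares text; the others are simple arithmetic.

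**1. Commitments against tables**

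| Protocol 12.4.1.1 | SAP counterpart | Declared in SAP 3.10? |
|---|---|---|
| Primary safety variables, iv PK Period, SS-iv | None on the SS-iv; the iv PK Period appears only within the SS by-period tables | No |
| AEs by study period, SS | By-period tables on the SS | Not needed |
| AEs by infusion epoch, SS-iv | Table by time since infusion, SS-iv | Yes |

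The SAP change logs for versions 3.0 to 5.0 do not mention the first row either.

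**2. What the change of set does to the numbers**

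The iv PK Period starts at the first iv dose (SAP 3.2.5), so every subject with an event in it is in the SS-iv. The numerators are therefore the same on both sets. A percentage can differ only through the denominator, by the ratio N/(N + k), where N is the SS-iv count and k the number of subjects who took oral BRV but no infusion. The documents do not give k; I assume 1 to 5, with the whole SS as denominator.

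- Overall, N about 50: 50/51 = 0.98 for k = 1; 50/55 = 0.91 for k = 5.
- One cohort, N about 12: 12/13 = 0.92 for k = 1.
- k = 0: ratio 1. SAP 3.1 then shows tables on the SS-iv only, and the mismatch disappears.

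Oral-only subjects received neither mode. If columns follow the mode received, the 15-minute and bolus columns hold the same subjects on both sets.

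**3. The >5 to 15 minute bin**

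The bin is 10 minutes wide. The 15-minute infusion may run 12 to 18 minutes; the bolus lasts up to 2 minutes (protocol Table 7-1).

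- 12-minute infusion: (12 − 5)/10 = 70% of the bin is during infusion.
- 15 to 18 minutes: (15 − 5)/10 = 100%.
- Bolus: finished before minute 5, so 0%.

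The 0 to 5 minute bin has a milder form of the same problem: all of it lies within a 15-minute infusion, and at most 2/5 = 40% within a bolus.

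**4. Can the time-since-infusion table stand in for the iv PK Period summary?**

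The period lasts (n − 1) × dosing gap + 12 h, with a gap of 10 to 14 h. That is 12 h for one dose and 22 to 26 h for two. Bins up to 12 h cover 12/12 = 100% for one dose and at least 24/26 = 92% for two. However, a subject can appear in several bins, so counts across bins cannot be added to a period total. The last bin (>12 h) can also mix time between doses with follow-up.

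**5. Why Follow-up should stay beside the iv PK Period**

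The iv PK Period ends 12 h (0.5 day) after the start of the last iv dose, and TC-1 is 1 to 3 days after that dose. The share of the interval to TC-1 that falls after the period is 0.5/1 = 50% to 2.5/3 = 83%. TC-1 exists to collect infusion-related AEs.

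**The case against.** The strongest defence is that the content is already planned and only the set label differs. The SS by-period tables give iv PK Period counts by cohort and infusion duration. SAP 3.1 allows a denominator suited to the analysis, so SS-iv denominators could be used for that column without contradiction. All of this stands, and it is why the point is minor.

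Withdrawals due to AEs are also largely covered. SAP 10.2.1 tabulates TEAEs leading to discontinuation on the SS-iv by cohort and infusion duration, and SAP 5.1 gives reasons for discontinuing during the iv PK Period on the SS-iv, though only overall. The all-period tables themselves fit a variable defined over the whole study.

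On the time-since-infusion table, the SAP 3.1 default adds infusion duration unless stated otherwise. That may be the intention. But neighbouring tables in SAP 10.2.1 name infusion duration explicitly and this one does not, so a programmer could reasonably leave it out.

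A reader might infer two stronger conclusions:

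- **The iv PK Period safety data will be missing, or the comparison of modes is biased.** The documents do not support this. The events are reported, the mode columns should hold the same subjects, and all summaries are descriptive.
- **Pre-infusion events swamp the all-period tables.** For OLB/RxB subjects who move to the long-term study after 1 to 2 doses, pre-infusion time is 1/(1 + 1.083 + 2.5) = 22% to 10/(10 + 0.5 + 0.5) = 91% of TEAE time. These are shares of time, not of events, and the by-period tables already separate those TEAEs.

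**Conclusion.** The inconsistency holds on the text. The protocol specifies an iv PK Period summary of the primary safety variables on the SS-iv; SAP 10.2.1 provides it only within SS tables, and SAP 3.10 does not declare this. The numerical effect is confined to the all-subjects and cohort denominators: none without oral-only subjects, and otherwise 0.98 to 0.91 times overall. That range assumes 1 to 5 such subjects and whole-SS denominators. That the mode columns are unaffected assumes they follow the mode received.

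The time-since-infusion table is the better reason to edit the section. As listed, it may pool modes in a bin that is 70% to 100% during infusion for one and 0% for the other. The SAP also does not say that TEAEs before the first infusion, which have no previous infusion to be timed from, are outside it.

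Severity: minor. No decision rule depends on either gap.

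**What to change.** 1. In SAP 10.2.1, list the time-since-infusion table for all subjects, by age cohort and by infusion duration. Add that TEAEs with onset before the first infusion are not in it and appear in the by-period tables.
2. In SAP 10.2.1, produce the by-period tables of TEAEs and of TEAEs leading to study discontinuation on the SS-iv, by cohort and infusion duration, and identify their iv PK Period column as the summary in protocol 12.4.1.1. Alternatively, keep the SS tables and use SS-iv denominators for that column. Either way, keep the Follow-up column alongside and retain the all-period SS-iv tables.
3. Record any remaining difference from protocol 12.4.1.1 in SAP 3.10.

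An SS-iv version of the serious TEAE table is optional, as are those for maximum intensity and maximum relationship.

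The cost is about two sentences in SAP 10.2.1, a line in 3.10 if needed, and existing programs rerun on data already collected. The downside is a few more descriptive tables with small cells: 12/2 = about 6 subjects per cohort and mode.

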5 STUDY DESIGN

5.1 Study description

EP0065 is a Phase 2 multicenter, open-label study to evaluate the PK, safety, and tolerability of iv BRV administered as a 15-minute iv infusion and an iv bolus (up to 2-minute infusion) in subjects ≥ 1 month to < 16 years of age with epilepsy.

It is planned for approximately 50 enrolled subjects to receive iv BRV in the following age-based cohorts (approximately 12 subjects/cohort):

- Cohort 1: ≥ 12 to < 16 years
- Cohort 2: ≥ 6 years to < 12 years
- Cohort 3: ≥ 2 to < 6 years
- Cohort 4: 1 month to < 2 years

The following subjects will be eligible for enrollment in EP0065:

- QLB subjects: currently receiving oral BRV as participants in a long-term, open-label study
- RxB subjects: currently receiving prescribed oral BRV from commercial supply
- IOB subjects: not currently receiving BRV; first dose of BRV in EP0065 will be oral tablet or solution
- IIB subjects: not currently receiving BRV; first dose of BRV in EP0065 will be by iv infusion

For OLB and RxB subjects, the maximum BRV dose is 5mg/kg/day (rounded). For IOB and IIB subjects, the maximum BRV dose is 4mg/kg/day. **Throughout the study, no subject may receive a dose greater than BRV 200mg/day.** Subjects will receive oral BRV (tablets or oral solution) in equally divided doses; BRV oral solution may be given by enteric administration (eg, by feeding tube) based on subject need.

The EP0065 study periods and visits are described below. The PK assessments will be made during the iv PK Period only and safety data will be collected throughout the study, with intensive collection of safety data with each iv BRV dose administered. A Schedule of Study Assessments is provided for the Screening through iv PK Periods in [Table 5-1](#) and for the Down-Titration Period and Safety (BRV-free) Periods (for subjects not continuing BRV) in [Table 5-4](#).

Screening Period (1 to 10 days)

During the Screening Period, the OLB and RxB subjects will continue treatment with oral BRV using their assigned open-label study supply or prescribed commercial supply, respectively. The IOB and IIB subjects will not receive BRV during this period.

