## 3 DATA ANALYSIS CONSIDERATIONS

### 3.1 General presentation of summaries and analyses

Statistical analysis and generation of tables, figures, subject data listings, and statistical output will be carried out using SAS Version 9.3 or higher. All summaries will be descriptive; no statistical hypothesis testing is planned. All tables and listings will use Courier New font size 9.

Tables, figures and listings (TFL) will be displayed for the defined analysis sets. If the Safety Set (SS) and the Safety Set-iv (SS-iv) consist of the same number of subjects, TFLs will only be presented for the SS-iv.

For categorical parameters, the number and percentage of subjects in each category will be presented. The denominator for percentages will be based on the number of subjects appropriate for the purpose of the analysis. Unless otherwise noted, all percentages will be displayed to 1 decimal place. No percentage will be displayed for zero counts, and no decimal will be presented when the percentage is 100%.

For continuous parameters, descriptive statistics will include number of subjects (n), mean, standard deviation (SD), median, minimum, and maximum, unless otherwise stated.

Decimal places for descriptive statistics will always apply the following rules unless otherwise stated:

- “n” will be an integer
- Mean, SD, geometric mean, and median will use 1 additional decimal place compared to the original data
- CV [%] will be presented with 1 decimal place
- Minimum and maximum will have the same number of decimal places as the original value

However, the maximum number of decimals displayed will not exceed 4.

All summaries, unless otherwise stated, will be presented overall for all subjects, by age cohorts (Cohort 1:  $\geq 12$  to  $< 16$  years, Cohort 2:  $\geq 6$  years to  $< 12$  years, Cohort 3:  $\geq 2$  to  $< 6$  years, Cohort 4:  $\geq 1$  month to  $< 2$  years), and by infusion duration (15-minute iv infusion and iv bolus (up to 2-minute infusion)). Selected tables will be provided in addition by subject groups (OLB, RxB and IOB combined, and IIB), or by scheduled assessment timepoints as defined in [Section 4.8](#).

Selected summaries will be repeated by the country of enrollment (Hungary and rest of the World).

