### 3.2.5 Analysis periods

This study consists of a Screening Period, an IOB Treatment Period, an iv PK Period, a Follow-up Period and a Safety (BRV-free) Period, see [Section 2.3](#) for more details on these periods.

Start of Screening Period is defined as the date of enrollment and end of Screening Period is defined as immediately before first allocated BRV treatment.

Start of IOB Treatment Period is defined as the date of first allocated oral BRV treatment and end of IOB Treatment Period is defined as immediately before first iv BRV treatment.

Start of iv PK Period is defined as the date and time of first allocated iv BRV treatment and end of iv PK Period is defined as 12 hours after start of last iv BRV treatment.

Start of Follow-up Period is defined as 12 hours after start of last iv BRV treatment and end of Follow-up Period is defined for the following scenarios:

- Subjects who transition study: as TC-1
- Subjects who do not transition and do not down-titrate: as end of study
- Subjects who down-titrate: as 12 hours after start of last down-titration treatment.

Only subjects who down-titrate have a Safety (BRV-free) Period. Start of Safety Period is defined as immediately after the end of Follow-up Period (>12 hours after start of last down-titration treatment) and end is defined as end of study.

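### The subject-group AE tables compare percentages taken over unequal TEAE windows, so the groups are not comparable, and the direction of the net distortion is not known

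*SAP*

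**What the plan says.** **Periods counted.** SAP 10.2.1 sets the default: "All summaries are for all study periods combined", unless otherwise indicated. Under it, four SS-iv tables are split by subject group: the AE Overview, TEAEs, TEAEs leading to study discontinuation, and serious TEAEs. The Overview and TEAE tables are also produced by country (Hungary and rest of the World) and subject group.

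**Columns.** SAP 3.1: "Selected tables will be provided in addition by subject groups (OLB, RxB and IOB combined, and IIB". SAP 9.1 uses the same grouping for PK and makes clear that IIB stands alone.

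**Where the TEAE window opens.** SAP 10.2: "all AEs are treatment emergent for RxB and OLB subjects; all AEs on or after the IOB Treatment Period are treatment emergent for IOB subjects"; and "all AEs on or after the iv PK Period are treatment emergent for IIB subjects". Protocol 5.1 gives the "Screening Period (1 to 10 days"), during which OLB and RxB children are on oral BRV, and an IOB Treatment Period of 2 to 10 days.

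**Where it closes.** SAP 3.2.5 ends Follow-up differently by route out of the study. One case is "Subjects who transition study: as TC-1". Children who down-titrate stay in Follow-up until 12 hours after the last taper dose starts and then enter the Safety Period. Protocol 5.1 allows up to 4 weeks of taper and 2 weeks free of BRV.

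**What else is planned.** SAP 10.2.1 also gives TEAEs, TEAEs leading to discontinuation and serious TEAEs by study period and subject group, on the SS, with each event assigned to its period of onset. Protocol 12.4.1.1 asks for the primary safety variables to be summarized for the iv PK Period on the SS-iv. SAP 3.10 lists changes to the protocol's analyses, but not the move to all periods combined.

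**The concern.** The subject-group split is where a reader would look to see whether children whose first BRV dose is intravenous tolerate it as well as children already on oral BRV. An event during Screening is a TEAE in an OLB child and a pre-treatment event in an IIB child. Every child in the combined OLB, RxB and IOB column brings pre-infusion time into the count, and no IIB child does. The windows also end at different times, depending on whether the child transfers or tapers. Two percentages set side by side could then differ with no difference in tolerability, or agree despite one. AEs and withdrawals due to AEs are the primary safety variables, so these tables will be read.

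**Working it through.** **1. Check the period lengths against the protocol's own totals (5.1.1).**
- Longest study duration (IOB): 10 Screening + 10 IOB + 6 iv PK + 28 taper + 14 Safety = 68 days. The protocol says 68.
- Longest BRV administration: 10 oral + 6 iv PK + 28 taper = 44 days. The protocol says 44.

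**2. Pre-infusion days inside the TEAE window.**

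| Group | Window opens | Days before first infusion |
|---|---|---|
| OLB, RxB | first Screening day | 1 to 10 |
| IOB | first oral BRV | 2 to 10 |
| IIB | first infusion | 0 |

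**3. Length of the window relative to IIB, up to TC-1.** TC-1 falls on Day 2 to Day 9 (Protocol 8.4). Let P be the days from first infusion to TC-1 and S the pre-infusion days; the ratio is (P + S)/P.

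| P | S = 1 | S = 2 | S = 10 |
|---|---|---|---|
| 2 | 1.50 | 2.00 | 6.00 |
| 4 | 1.25 | 1.50 | 3.50 |
| 9 | 1.11 | 1.22 | 2.11 |

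**4. Effect on incidence.** The documents give no AE rate. Assume a constant daily hazard h of a first TEAE, the same in every group, so that incidence = 1 − exp(−h × days). With P = 4:

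| h per day | IIB (4 days) | S = 1 (5 days) | S = 10 (14 days) |
|---|---|---|---|
| 0.01 | 3.9% | 4.9% | 13.1% |
| 0.03 | 11.3% | 13.9% | 34.3% |
| 0.05 | 18.1% | 22.1% | 50.3% |

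Taken alone, this part favours IIB.

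**5. The other end of the window can reverse it.** An IIB child with P = 4, a 7-day taper and the 14-day Safety Period has 4 + 7 + 14 = 25 days. At h = 0.03 that gives 52.8%, against 34.3% for an OLB child with 10 Screening days who leaves at TC-1. If the taper starts straight after the last infusion, it overlaps the 1 to 3 days to TC-1. The window is then at least 22 days: 1 − exp(−0.66) = 48.3%, still the higher figure.

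For mean window length, a 5-day pre-infusion excess is cancelled if the share of children who taper is higher in IIB by 5/42 = 12 percentage points (28 + 14 extra days) or 5/21 = 24 points (7 + 14 extra days). The documents do not give the share tapering by group.

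**6. Which results have a version on a common window?**

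| Result by subject group | By-period version |
|---|---|
| TEAEs; TEAEs leading to discontinuation; serious TEAEs | yes, on the SS |
| Overview rows such as drug-related, severe, dose change, permanent BRV withdrawal | none |
| Maximum intensity, maximum relationship | by period, but not by subject group |
| Overview and TEAEs by country | none |
| TEAEs by time since infusion | not by subject group |

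The iv PK Period ends 12 hours after the last infusion starts (SAP 3.2.5). Events collected at TC-1, the contact meant for infusion-related AEs, can therefore fall in Follow-up, which also contains any taper. A child with events in two periods counts in both, so percentages cannot be added across periods to recover the span from first infusion to TC-1.

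**The case against.** Much of this is already handled. For TEAEs, discontinuations and serious TEAEs, the by-period tables have an iv PK column defined identically for every group, which is close to like for like. They use the SS, so children who took oral BRV but never had an infusion may be in the denominator; if the SS and SS-iv are the same size, SAP 3.1 presents the SS-iv only. The Overview's row for any AE opens at consent, so it starts at the same point for OLB, RxB and IIB, although IOB still has an extra period. The listings give onset and relationship for each event in about 50 children. The comparison is descriptive and non-randomized and is not a stated objective. This stands, and it limits the gap to the results without a by-period subject-group version.

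The constant hazard is also open to doubt. Entrants must be on a stable AED regimen for at least 7 days before Screening, and safety collection is most intensive around each infusion, so pre-infusion days may yield fewer events per day. The incidences above are illustrations, not estimates.

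A reader might go further and infer that starting BRV intravenously will look safer than it is. The documents do not support that. No IIB event after the first BRV dose is left out; it is the other groups' windows that are longer. The unequal closing times can also outweigh the unequal opening times. Nor is the pre-infusion share always large: with 1 Screening day, 6 iv days and 42 days of taper and Safety time it is 1/49, about 2%.

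**Conclusion.** The point holds as one of comparability. The pooled subject-group percentages cover windows that differ by design: 1 to 10 pre-infusion days for OLB and RxB, 2 to 10 for IOB and none for IIB, with closing times that differ by up to 42 days. Up to TC-1, the window for a child with pre-infusion time is 1.11 to 6.0 times the IIB window across the cases shown. That ratio follows from the period lengths; any difference in incidence rests on an assumed AE rate, and the net direction depends on taper shares that the documents do not give. The practical gap is in the Overview rows with no by-period subject-group version and in the by-country tables. Because Protocol 12.4.1.1 names the iv PK Period on the SS-iv, and SAP 3.10 does not record the change, this also needs reconciling on paper.

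**What to change.** In SAP 10.2.1:

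- Keep the all-period subject-group tables, so that taper and later events stay visible, with a footnote saying where the TEAE window opens and closes for each group.
- Add SS-iv versions of the subject-group AE tables, including the Overview and the by-country tables, restricted to onset in the iv PK Period as Protocol 12.4.1.1 states.
- Add a second cut from first infusion to TC-1, to pick up delayed infusion-related AEs, with a stated rule for a missed TC-1.
- List in SAP 3.10 any departure from Protocol 12.4.1.1 that remains.

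Both cuts remove the pre-infusion excess in every group: at h = 0.03 over 4 days, each group shows 11.3%. Window length still varies between children with the number of infusions and the date of TC-1, but no longer by definition of the group. The cost is SAP wording, an onset filter on data already collected, and a few extra tables whose counts will not match the all-period tables.
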